Our primary process-focused outcome for Aim 4 is **micro-decision making**. Through focus group interviews with key ICU Liberation Collaborative participants, we specifically aim to describe micro-decision making about ABCDEF bundle implementation and to determine how and to what extent patient preferences are ascertained and considered when implementing evidenced-based ICU pain, sedation, MV liberation, and early mobility practices.

Conceptual Framework. Our approach is guided by the Consolidated Framework for Implementation Research (CFIR),⁴⁴ which provides a comprehensive taxonomy of operationally defined constructs from multiple disciplines (e.g., psychology, sociology) that are likely to influence implementation of complex programs; 39 constructs are organized across 5 major domains that interact to influence implementation effectiveness.

Aim 1: Estimate the effects of patient-level characteristics on ABCDEF bundle adoption.

Design and Rationale. In Aim 1, we will use existing SCCM ICU Liberation Collaborative data to estimate the effects that various non-modifiable factors exhibited by ICU adults at admission (i.e., patient-level characteristics) have on ABCDEF bundle adoption. Previous surveys, qualitative investigations, and systematic reviews reported that certain patient-level characteristics (e.g., instability, patient weight/size) may impede bundle delivery, but these studies were limited in use of self-reported (vs. actual) rates of implementation.^{35,36,125,126,128} Findings from this aim will for the first time objectively distinguish which patient-level characteristics affect delivery of the overall bundle and its individual elements. Findings will have immediate relevance to patient care by aiding in the design of specific implementation strategies focused on overcoming patient-level barriers.

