Setting and Sample. **Included** in the Collaborative were adults who were (1) initially admitted to a participating ICU and (2) designated as needing ICU level of care. Patients previously admitted to a non-participating ICU during their current hospitalization were not included. “ICU level of care” was defined as patients who (1) needed intensive medical and/or nursing care that not could not be delivered in a step-down and/or medical/surgical unit, (2) were managed by an ICU team, or (3) did not have transfer orders written or downgraded to a lower level of care. **Excluded** were patients who (1) died or were discharged within 24 hours of ICU admission or (2) were undergoing life support withdrawal and/or documented comfort care only within 24 hours of ICU admission.

Aim 1 data consist of **15,226** patients who spent 24 hours in a participating ICU (~**49,000 ICU patient-days**). Our sample includes patients on and off MV, ranging from 18-90+ years old, admitted with a variety of diagnoses. Of the 15,226 patients, 63% (n = 9619) were hospitalized in academic medical centers and admitted to mixed medical/surgical (56%), medical (18%), surgical/trauma (12%), neurologic (5%), or cardiac/surgical (10%) ICUs.

Procedures and Data Sources. The Vanderbilt University Medical Center Institutional Review Board (IRB) served as the Coordinating Center IRB and approved the SCCM ICU Liberation Collaborative QI project. All Collaborative participants acquired site-specific IRB evaluation and approval. No identifiable data were collected. All data were collected by standardized medical record review and anonymous staff surveys and were managed using a secure, web-based application designed for validated data entry, transmission, and storage (Research Electronic Data Capture [REDCap], Vanderbilt University, 2016 - grant support [(UL1 TR000445 from NCATS/NIH]).

[figure not shown]

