Local staff who attended a training webinar and as-needed support from SCCM managers entered de-identified data into the collaborative database at their individual hospitals. Data were collected retrospectively during a 6-month baseline period (January 2015-June 2015) and prospectively during a 14-month implementation period (January 2016-March 2017). During the baseline (pre-Collaborative) period, staff from each site entered data on the first 5 consecutively admitted ICU patients each month (30 baseline patients per site). Throughout the implementation period, site staff collected data on the first 15 consecutively admitted patients per month. For each patient, daily data were collected for a maximum of seven ICU days (average of 3.3 ICU-days per patient) or until patients transferred out of the ICU, were designated non-ICU status, or died.

Measures. Patient-level variables include: age, sex, race, ethnicity, language, body mass index (BMI), admitting diagnosis, severity of illness, and preadmission residence and mobility status. The severity of illness scores collected in the Collaborative included the Acute Physiology and Chronic Health Evaluation (APACHE) II,¹³⁰ APACHE III,¹³¹ and APACHE IV¹³² referent to the patient's status at the time of ICU admission.

Data analysis. We will conduct similar analyses for each of the performance measures (performed vs. not performed), including complete, proportional, and each element performance. We will first use descriptive statistics to examine data distribution, check for outliers, and summarize patient characteristics. Bivariate tests (e.g., *t* test or Chi-square statistics) will be used to compare patient characteristics in the pre-Collaborative and Collaborative periods.

Using multilevel segmented logistic regression modeling for interrupted time series data, we can model the likelihood of bundle performance change over time, both before and during the periods of Collaborative implementation. **Figure 2** shows a hypothetical example. The basic form of the level-1 model (Figure x, solid black line) can be written as $\text{Logit}(Y_{ij}) = \beta_{0j} +$

Figure 2. Segmented logistic regression for ITS data-A hypothetical example

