β_{1j} Month + β_{2j} Imp + β_{3j} Month * Imp + e_{ij} , where (1) Logit(Y_{ij}) denotes the logit (or log-odds) of receiving bundle performance for the i^{th} ICU-day of the j^{th} patient; (2) Month is the month indicator of the study period (a total of 20 months coded as -5 to 0 for pre-implementation period and 1 to 14 for implementation period); and (3) Imp denotes an indicator variable coded as 0 for pre-implementation period and 1 for the implementation period. Therefore, Logit(Y_{ij}) is modeled as a linear function of $\beta_{0j} + \beta_{1j}$ Month for the pre-implementation period and $(\beta_{0j} + \beta_{2j}) + (\beta_{1j} + \beta_{3j})$ Month for the implementation period. β_{2j} and β_{3j} are the estimates of level and slope changes due to the intervention implementation. A significant level change (β_{2j}) indicates an immediate change in the level of bundle performance at the initiation of intervention implementation. A significant slope change (β_{3j}) indicates different trends over time during the pre- vs. post-implementation periods. Under the multilevel modeling framework, level-2 models will fit β_{0j} , β_{1j} , β_{2j} , and β_{3j} each as a linear function of fixed-effects of patient characteristics and patient-specific random effects. The patient-specific random terms allow for adjustment of within-patient clustering of ICU-days. Take patient gender as an example. From the combined multilevel segmented logistic regression model, we will (1) estimate the overall trends during the pre- and implementation periods (solid black lines); (2) derive fixed-effect estimates by patient characteristics (Figure 4, long dashed line and short dashed line for each gender); (3) test the significance of hypothesized subgroup differences (e.g., older age, obese, and non-English speaking) in the these estimates; and (4) include patient-specific random terms to allow for variability by patients (patient-specific lines not shown in Figure 4). The model can be simplified if supported by the preliminary results. For example, if the initial analyses for an outcome (e.g., element E performance) suggest that (1) there are no significant level change and slope change for both male and female patients and (2) the overall increasing trend over time does not differ by patient gender, we can reduce the model to a parsimonious form using multilevel logistic regression to model the probability of having an outcome as a function of fixed effect of patient gender, fixed effect of time, and patient-specific random effects. We can also further extend the model to (1) include multiple patient characteristics simultaneously in the model to generate multivariable adjusted estimates, (2) perform curve fitting for linear or non-linear trend, and (3) adjust for additional clustering (e.g., within-organization clustering). The above desried multilevel segmented logistic regression approach will be applied to analyzing complete and element bundle performance measures. For proportional bundle performance, we will use multilevel segmented Poisson regression instead.

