
Power analysis. We used the simulated-based power calculation method by Zhang et al.¹³³ for interrupted time series analysis to conduct power analysis for Aim 1. With the expected ~49,000 ICU-days of ~15,000 patients in 68 ICUs, we generated 1,000 simulations with various patient subgroup distributions and proportion of ICU days with bundle performance during the pre-implementation and implementation periods. Our preliminary analyses of the pre-implementation period data suggest that the probability of bundle performance ranged from 0.05 (for complete bundle performance) to 0.60 (for performance of element A) at the end of the pre-implementation period and a monthly increase in the probability ranged from zero (for element E) to 0.05 (for element D). To be conservative in power calculation, we used a probability of 0.05 for the level and a 0.05 monthly increase in the probability for the slope in the pre-implementation period. Our power analysis suggested that our data will have 80% power to detect an odds ratio (OR) of 1.25 (corresponding to an increase of 0.02 in the probability of receiving bundle performance) and 80% power to detect a slope change, with an OR of 1.52 corresponding to pre- vs. post-difference of 0.03 in the monthly increase of the probability of receiving bundle care. Based on our preliminary data, we reasonably assumed an autocorrelation of 0.5 under the first order auto-regressive covariance structure, a within-patient correlation of 0.5, and a within-hospital correlation of 0.6 in our simulation-based power calculation. Under the same assumptions, we also conducted power analyses on the effects of patient characteristics on the level and slope changes. For patient characteristics with 20:80 distribution, our sample size will have 80% power to detect an OR of 1.73 for the effect of patient characteristics on level change and 80% power to detect an OR of 2.65 for the effect of patient characteristic on slope change. The above power calculation is the most conservative scenario. The study power will be greater than 80% for other cases (e.g., pre-probability of 0.5, patient characteristics with 50:50 distribution). Regardless of study power, we will report point estimates, 95% confidence intervals, and use clinical significance to guide results interpretation. All above calculations were based on multilevel segmented logistic regression with a 0.05 two-sided significance level and adjusted for data dependencies described above.

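### Aim 1 asks how each patient characteristic affects bundle adoption, but the implementation-period effect is neither named as the target nor powered

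*Combined protocol and SAP*

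**What the plan says.** All references are to the combined protocol and SAP.

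- **The question.** The aim is to "Estimate the effects of patient-level characteristics on ABCDEF bundle adoption". Aim 1, Design and Rationale, says the findings will "objectively distinguish which patient-level characteristics affect delivery of the overall bundle and its individual elements".
- **The model.** Aim 1, Data analysis, fits a segmented logistic model with an intercept, Month, an implementation indicator and their product. Month is coded as "a total of 20 months coded as -5 to 0 for pre-implementation period and 1 to 14 for implementation period". All four coefficients are then modelled "each as a linear function of fixed-effects of patient characteristics and patient-specific random effects". Lines by subgroup will be derived, and hypothesized subgroup differences in the estimates will be tested.
- **The reduced model.** The same section allows simplification to a single fixed effect of the characteristic plus a time effect. Its example requires no significant level or slope change in either sex, and a trend that does not differ by sex.
- **Power.** For a 20:80 characteristic, Aim 1, Power analysis, states "80% power to detect an OR of 1.73 for the effect of patient characteristics on level change" and a corresponding OR of 2.65 for slope change. It gives no figure for an overall or implementation-period effect. It does promise point estimates and 95% confidence intervals whatever the power.
- **Sampling.** Under Aim 1, Procedures and Data Sources, at baseline "staff from each site entered data on the first 5 consecutively admitted ICU patients each month (30 baseline patients per site"; during implementation, "site staff collected data on the first 15 consecutively admitted patients per month".
- **Downstream use.** Aim 2, Data Analysis, keeps the significant Aim 1 characteristics as case-mix covariates. It does not say which of the four terms decides significance.

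**The concern.** The powered tests ask whether the gap between two kinds of patient changes when the Collaborative starts. The aim asks whether there is a gap. These are different questions. A characteristic that holds delivery back to the same degree before and after implementation is exactly the sort of barrier the Design and Rationale describes, yet its true value is zero on both powered terms.

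Two things are at stake. Stable barriers of modest size could be passed over when strategies are designed to overcome patient-level barriers. They could also be left out of the Aim 2 case-mix adjustment, and so out of the adjusted rates used to rank the top five and bottom five ICUs.

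**Working it through.** **1. What the coefficients mean.** Write g0, g1, g2, g3 for a characteristic's effects on baseline level, baseline slope, level change and slope change. Its effect at implementation month t is g0 + g2 + t(g1 + g3). Averaged over t = 1 to 14 (mean 7.5), it is g0 + g2 + 7.5(g1 + g3). No single coefficient equals this. For a barrier constant on the logit scale, g1 = g2 = g3 = 0 and only g0 is non-zero.

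**2. Where g0 gets its information.** In the full model the baseline line is fitted from baseline patients only: at most 68 × 30 = 2,040, or 2,040/15,226 = 13.4%. The month coding places g0 at month 0, the end of that line.

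**3. Relative standard errors, equal information per patient.** There are 68 × 5 = 340 patients a month for 6 baseline months and 68 × 15 = 1,020 a month for 14 implementation months. The sums of squared month deviations are 17.5 and 227.5. A factor for the characteristic's prevalence is common to all terms and cancels in ratios.

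- g0: √[(1/340)(1/6 + 2.5²/17.5)] = √(0.5238/340) = 0.0393
- Level change g2: √[0.5238/340 + (1/1,020)(1/14 + 7.5²/227.5)] = 0.0430
- Implementation average: √[1/(14 × 1,020)] = 0.0084

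The ratios are 4.7 (g0) and 5.1 (level change). The schedule implies 240 × 68 = 16,320 patients, more than the 15,226 reported. With 15,226 − 2,040 = 13,186 implementation patients the average has SE 1/√13,186 = 0.0087, and the ratios are 4.5 and 5.0.

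**4. Trying to reproduce the plan's figures.** The simulation model behind 1.73 and 2.65 is not given in full. Read literally, a probability of 0.05 at the end of baseline rising by 0.05 a month gives 0.05 − 5 × 0.05 = −0.20 at month −5. The closest variant tried starts at 0.05 in month −5, reaches 0.30 in month 0, and uses the stated within-patient correlation of 0.5. It gives a detectable level-change OR of 1.77 to 1.78 (power 0.76 to 0.77 at 1.73), which is near but not a match. No variant gives 2.65 as a per-month slope OR; the detectable values were about 1.10 to 1.62. Step 5 therefore does not use the stated ORs.

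**5. Letting information vary with the performance probability p.** Each month is weighted by patients × p(1 − p), with 340 and 13,186/14 patients a month. The detectable OR is exp[(1.96 + 0.84) × SE], with SE² = v × (1/0.2 + 1/0.8) × D/d. Here v is the relative variance, d = 49,000/15,226 = 3.22 days per patient, and D = 1 + 2.22 × 0.5 = 2.11. The paths for p are assumptions.

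| Assumed path for p | √v, g0 | √v, average | Ratio | Detectable OR, g0 | Detectable OR, average |
|---|---|---|---|---|---|
| 0.05 throughout | 0.180 | 0.040 | 4.5 | 2.78 | 1.25 |
| 0.05 baseline, rising to 0.13 by month 14 | 0.180 | 0.031 | 5.8 | 2.78 | 1.19 |
| 0.05 baseline, then 0.05 + 0.05t, cap 0.75 | 0.180 | 0.020 | 9.2 | 2.78 | 1.12 |
| 0.01 rising to 0.05 baseline, then as above | 0.198 | 0.020 | 10.1 | 3.07 | 1.12 |
| 0.05 to 0.30 baseline, then 0.32 + 0.05t, cap 0.95 | 0.093 | 0.023 | 4.1 | 1.69 | 1.14 |
| 0.60 baseline, 0.70 implementation | 0.080 | 0.019 | 4.2 | 1.57 | 1.11 |
| 0.50 baseline, 0.90 implementation | 0.079 | 0.029 | 2.7 | 1.56 | 1.18 |

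The ratio runs from roughly 3 to 10. Two other settings were also tried: D = 1 (independent days), and D multiplied by 1 − 0.6 to allow for the stated within-hospital correlation. Over all of these the detectable OR is 1.07 to 1.25 for the average and 1.33 to 3.07 for g0.

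**6. Simulation of a constant barrier.** The assumptions were conditional OR 0.75, 20% prevalence, and performance of about 7% at baseline and 12% in implementation, with 300 runs. Power was 10% for g0, 7% for level change and 6% for slope change, against about 100% for one common term. The two change figures are near the 5% error rate because their true value is zero. At OR 0.5, power for g0 was 37%.

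**7. The reduced model against the preliminary results.** Preliminary Data reports a slope change for complete performance (0.6% a month, P = 0.038) and a level change for proportional performance (3.8%, P = 0.026). Both conflict with the example's condition of no level or slope change. Those results are for all patients together, not by subgroup.

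**The case against.** A reader might infer that the plan yields no estimate of a characteristic's effect on delivery. The documents do not support that. Aim 1, Data analysis, derives a line for each subgroup and tests subgroup differences, and the implementation-period gap can be computed from those lines. Nor does the text say that testing must go coefficient by coefficient. What stands is that no section names the contrast or powers it.

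A reader might also infer that stable barriers will be reported as non-significant. That goes too far. A large barrier can be detected on the baseline-level term, and the reduced model would give one pooled coefficient from all patients. Its conditions are offered as an example, and element E is named there as a candidate. But the reduction is optional, depends on non-significant results in tests of limited power, and has example conditions that conflict with the preliminary results for two of the measures.

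It is tempting to scale the stated OR of 1.73 by the SE ratios (1.73 × the 0.0084/0.0430 ratio on the log scale gives 1.11) and call that the plan's own figure. The same scaling gives a slope-change OR of about exp(0.548 × 0.0131/0.0430) = 1.18, against the stated 2.65. So it is not the plan's scaling, and a single value would be falsely precise.

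Finally, whether subgroups gained differently is a legitimate adoption question, and the model is presented as one of change over time. That is a reason to keep the change terms. It does not supply the effect the aim asks for.

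**Conclusion.** The point holds as a gap between the aim and the named, powered quantities. The implementation-period effect of each characteristic is obtainable from the planned model but is not pre-specified as the target and has no power figure.

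In the full model, a barrier constant on the logit scale appears only in the baseline-level term. That term rests on at most 13.4% of patients, and its SE is roughly 3 to 10 times that of the implementation-average contrast. Power for modest stable barriers is therefore low if inference rests on the individual coefficients.

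The direction was the same on every path tried; the size depends on the assumed performance path. The figures also assume full baseline accrual, equal monthly counts, 20% prevalence in every month and a simple design effect. They apply to the logistic measures (complete and element performance), not to the Poisson model for proportional performance.

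**What to change.** For each characteristic and performance measure, pre-specify one main result: the adjusted difference averaged over the implementation months. The last implementation month is an alternative, since Aim 2, Data Analysis, already reads ICU rates there. Take it as a single contrast from the same fitted model and report it with a 95% CI.

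Give it its own power figure from the plan's simulation. The direct approximation above gives a detectable OR of 1.07 to 1.25 for a 20:80 characteristic, and scaling 1.73 over several paths gives 1.06 to 1.17, so a value between about 1.06 and 1.25 is to be expected for the average.

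Report the level-change and slope-change differences alongside, as effect modification over time. State in Aim 2 that this contrast, not the change terms alone, decides which characteristics carry into the risk adjustment.

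The cost is one contrast statement per characteristic and measure, one added output from the power simulation, and a sentence in each aim. No new data are needed.

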Based on our prior work,^{28,29,118} evidence-based professional behavioral change interventions and implementation strategies were shared and used by Collaborative members. For example, during the in-person meetings, the importance of providing audit and feedback, conducting cyclical small tests of change, changing record systems, and providing ongoing multimodal educational offerings to ICU staff were discussed. Sites were further encouraged to engage staff in local consensus discussions, develop a formal implementation and quality-monitoring plan, and identify and involve bundle champions, early adopters, local opinion leaders, and former ICU patients/families in the implementation process. The in-person meetings also helped to reinforce and provide beneficial strategies for facilitating effective ICU communication, collaboration, and cooperation. The heterogeneity in implementation strategies used by collaborative participants provides a rich and unique opportunity to learn what interventions are associated with greatest bundle adoption.

[figure not shown]
Our preliminary data demonstrate that ABCDEF bundle performance is associated with improved short-term outcomes. To date, we have explored the association between collaborative member's ABCDEF bundle performance and patient-, symptom-, and system-related outcomes (under-review). We defined bundle performance as either complete or proportional. This analysis included 15,226 critically ill adults with a variety of diagnoses who spent at least one full day in a participating ICU. Adjusting for a minimum of 18 *a priori* determined potential confounders, complete bundle performance was significantly associated with higher likelihood of ICU and hospital discharge and lower likelihood of hospital death within 7 days. Complete bundle performance was also significantly associated with lower likelihood of next day MV, coma, delirium, and physical restraint use and lower odds of ICU readmission and discharge to a facility other than home. Consistent with prior work,²⁹ our data also demonstrated a dose-response relationship between higher proportional bundle performance and improvements in each of the above clinical outcomes (all $p < 0.002$).

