Our preliminary data also show that collaborative participation resulted in significant but highly variable ABCDEF bundle adoption. Our next goal was to determine if collaborative participation led to increased bundle adoption. We were interested in exploring if some sites were "better" ABCDEF bundle adopters than others. The presence of a substantial amount of variability in our data would present us the opportunity to learn both from high- and low-bundle-performing sites. We calculated monthly rates of complete bundle performance, proportional bundle performance, and element-specific performance for the 17,258 patients across 49,109 full ICU days. We used segmented regression analysis for interrupted time series data to model the linear trend of bundle performance rates as a function of time for each segment (1-6 months pre-Collaborative involvement and 7-20 months during the Collaborative).

Complete bundle performance levels were low in the baseline (pre-Collaborative) period (i.e., < 4%). Complete bundle performance increased 2.0% (SE = 0.9%, $P = 0.057$) immediately after joining the Collaborative, and each month was associated with 0.6% greater increase (SE = 0.2%, $P = 0.038$) in complete bundle performance rates, compared to a relatively flat trend in the pre-Collaborative period. Proportional bundle performance rates also significantly increased by 3.8% (SE = 1.6%, $P = 0.026$) immediately after joining the Collaborative, then increased monthly at the same speed as the trend in the pre-Collaborative period (2%, SE = 0.4%, $P = 0.57$).

Bundle performance was highly variable among ICUs and across individual bundle elements; interquartile ranges of > 20% existed for all performance measures. (**Figure 1**) Elements A, C, D, and F were performed on average $\geq 70\%$ of the time at the end of the Collaborative:

Figure 1. Variation among ICUs in Unadjusted ABCDEF Bundle Performance Rates

adoption of elements B1, B2, and E (SATs, SBTs, and early mobility) proved far more challenging. For example, at the end of the Collaborative, an average $\leq 40\%$ of patients participated in early mobility and less than half of patients requiring MV received a daily SBT. Although overall performance was relatively poor, there were indeed some very good bundle performers.

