Data Analysis. The overall analytic strategy for Aim 2 will be the same as described for Aim 1. That is, using multilevel segmented logistic regression modeling for complete and element bundle performance and multilevel segmented Poisson regression for proportional performance. First, we will examine the variation across ICUs in bundle performance by adding ICU-specific random effects to the model. All significant patient-level characteristics from Aim 1 will remain in the model as covariates so that ICU-level estimates are risk-adjusted for patient case mix. From the model, we can (1) quantify the degree of ICU variation using the intra-class correlation (ICC); (2) derive the ICU-specific adjusted rates of bundle performance at the last month of implementation and examine their distribution (mean, variance, median, interquartile range, and range); and (3) rank the ICU-specific adjusted rates from low to high and identify the top 5 and bottom 5 ICUs with best and worst adjusted performance rates. Next, we will estimate the effects of organizational characteristic on bundle adoption by adding them as fixed effects to the model. Organizational survey at the post-implementation period will be estimated as fixed effects to model the level change (β_{2j}) and slope change (β_{3j}). While data from the pre-implementation period will be estimated as fixed effects to model pre-implementation level (β_{0j}), pre-implementation slope (β_{1j}), post-implementation level change (β_{2j}), and slope change (β_{3j}) (see **Data Analysis section for Aim 1**). Again, multilevel clustering (within-patient clustering of ICU days and within-ICU clustering of patients) will be adjusted in the model using random effects terms. As the provider-level data can be linked to specific ICUs, but not linkable to specific patient and patient ICU days, we will use multilevel modeling (level-1: time-point [pre- and post-survey], level-2: provider; level-3: ICU) to model the fixed effect of time, provider-level assessments (AITCS, HWEA,^{136,137} and ICU Care and Perceptions surveys), and their interactions on ICU-level adjusted performance rates. From the model, we can derive contrast estimates on the effect of change in

provider-level assessments on ICU-level bundle adoption. We will also extend the model to adjust for ICU-within-organization clustering.

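### Proportional bundle performance is capped at 100% but is given a Poisson model with no stated denominator, which distorts patient variance and blurs ICU-specific rates

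*Combined protocol and SAP*

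**What the plan says.** Aim 1, Data analysis, sets out a multilevel segmented logistic model for complete and element performance and then states: "For proportional bundle performance, we will use multilevel segmented Poisson regression instead". Aim 2, Data Analysis, carries the same split forward: "using multilevel segmented logistic regression modeling for complete and element bundle performance and multilevel segmented Poisson regression for proportional performance".

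The outcome is named but not defined. Preliminary Data says "We defined bundle performance as either complete or proportional" and gives neither numerator nor denominator. It does report the measure as a percentage: "Proportional bundle performance rates also significantly increased by 3.8" percent. The elements it lists are A, B1, B2, C, D, E and F. No offset, dispersion term, robust variance or bound on fitted values is mentioned.

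Aim 2 uses the model for an intra-class correlation, for adjusted ICU rates at the last month, and for a ranking that picks the top 5 and bottom 5 ICUs. ICU-level adjusted rates are also the outcome in the provider-survey model.

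**The concern.** The natural reading of the measure is k elements performed out of m eligible on an ICU-day. That is binomial-type data with a ceiling. A Poisson model has no ceiling, ties the variance to the mean, and with a log link lets a fitted share pass 1. Nothing in the stated plan corrects for this.

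At stake is one of the two overall adoption measures. The patient variance component, the ICU-specific rates that Aim 2 reports and reuses, and the meaning of the ICC all depend on this choice.

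**Working it through.** **The plan's own figures.** No figure in the protocol rests on the Poisson model. The nearest is the Aim 2 reliability figure: n = [0.8/0.2] × [0.7/0.3] = 9.33, rounded up to 10, which matches the text.

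**Inputs**
- Eligible elements: 7, or 5 on a day without ventilation (assumption: B1 and B2 do not then apply).
- Level at the end of the Collaborative (Preliminary Data): A, C, D, F at least 70%, E at most 40%, SBT below half. Taking 0.70, 0.40 and 0.50 for both SBT and SAT (the SAT value is assumed): (4×0.70 + 0.40 + 2×0.50)/7 = 0.60. Without B1 and B2: (4×0.70 + 0.40)/5 = 0.64. Range examined: 0.45 to 0.70.
- Size: 15,226/68 ≈ 224 patients per ICU, 3.3 days each.
- ICU spread, two versions. An interquartile range of 20 points gives a logit SD of about 0.6; the protocol says above 20%, so this is a floor. An ICC of 0.3 (Aim 2 power section, not specific to this outcome) gives √(3.29×0.3/0.7) = 1.19.
- Patient logit SD 0.4, 0.8, 1.2 and a 50:50 split of 5 and 7 eligible elements: assumed.

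**1. Variance.** The Poisson/binomial ratio is mp/[mp(1−p)] = 1/(1−p). With within-day correlation ρ, the true variance is mp(1−p)[1+(m−1)ρ], which equals the Poisson variance at ρ = p/[(1−p)(m−1)].

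| p | ratio at ρ = 0 | break-even ρ, m = 7 | m = 5 |
|---|---|---|---|
| 0.45 | 1.82 | 0.14 | 0.21 |
| 0.60 | 2.50 | 0.25 | 0.38 |
| 0.70 | 3.33 | 0.39 | 0.58 |

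Above break-even, Poisson variance is too small. At p = 0.60 the Poisson law also puts 6% (m = 7) to 8% (m = 5) of its mass above m.

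**2. Patient component.** To a first approximation with independent elements, fitted variance = true variance − 1/N, where N is the patient's element opportunities: 3.3×5 = 16.5 to 3.3×7 ≈ 23, so 1/N is about 0.04 to 0.06. Simulation (68 ICUs, about 15,000 patients, 20 months, Poisson with a log(eligible) offset) gave, on the log scale:
- independent elements: true SD 0.20, 0.40, 0.62 fitted as about 0.00, 0.20–0.25, 0.39–0.44;
- within-day correlation 0.35: true SD 0.20 and 0.30 fitted as 0.27 and 0.34.

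The sign of the error depends on the correlation.

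**3. ICU component.** N is about 224×3.3×6 ≈ 4,400, so 1/N is about 0.0002. Fitted SD was 0.233–0.245 against a realised 0.245, or 0–5% low.

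**4. ICU last-month rates** (12 simulated data sets)

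| | ICU logit SD 0.6 | ICU logit SD 1.19 |
|---|---|---|
| mean absolute error, Poisson | 2.7–3.3 points | 3.8–4.9 points |
| highest fitted rate, Poisson | 0.93–0.98 | 1.11–1.14 |
| highest true rate | 0.81–0.87 | 0.92–0.96 |
| ICUs above 100%, Poisson | 0 | 2–4 of 68 |

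The binomial-logit fit had errors of 0.6–1.8 points over both columns, and its highest rates stayed within 1 point of the truth. Top-5 and bottom-5 sets agreed between the two models in 4–5 of 5.

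**5. Level-change standard error** (24 data sets in each of six settings). Mean model SE was 0.0146, 0.0163, 0.0194, 0.0168, 0.0188, 0.0217; empirical SD was 0.0146, 0.0233, 0.0213, 0.0188, 0.0184, 0.0235. There is no inflation. In the second setting the model SE is 0.70 of the empirical SD, but an SD from 24 runs has a relative error of about 1/√46 = 0.15, so the run is too small to settle that.

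**6. If no offset is used.** With SAT and SBT at 0.45 (assumed), a ventilated day averages 2.8 + 0.4 + 0.9 = 4.1 of 7 (0.59), and a non-ventilated day 3.2 of 5 (0.64). The ratio of shares is 0.92; the ratio of counts is 4.1/3.2 = 1.28, the opposite direction.

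**7. ICC.** Assume ICU logit SD 0.5, patient 0.6, p = 0.6 and independent elements. A day-level ICC on the proportion scale is 0.19. A log-scale Poisson ICC with residual ln(1+1/μ) is 0.11–0.14. A latent-logit ICC is 0.25/(0.25+0.36+3.29) = 0.064. Here the scale matters more than the model, and Aim 2 names no scale.

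**The case against.** **The offset.** The protocol speaks of rates, which suggests a denominator, so its absence may be an omission in the text. That is fair: the confusion of ventilation with performance in step 6 is conditional. The simulations already gave Poisson the benefit of an offset.

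**The comparison favours the binomial model.** In step 4 the data were generated on the logit scale with independent elements, which is that model's own form. This stands, so the error figures are illustrative.

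**The near-zero patient SD is a small-variance case.** A logit SD of 0.4 is a latent correlation of 0.16/3.45 = 0.05, whereas the Aim 1 power section assumes 0.5 within patients. This also stands, though at SD 1.2 (1.44/4.73 = 0.30) the fitted value was still only 63–71% of the truth.

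**Stronger inferences a reader might draw.**
- *That residual variance is always overstated, so the analysis is merely conservative.* The Scientific Premise describes the elements as interdependent and gives no correlation. The direction cannot be read from the documents.
- *That the ICU variance is biased and the ICC understated.* Step 3 shows almost no ICU bias. Step 7 shows that an apparent fall from 0.19 to 0.11–0.14 compares two scales.
- *That confidence intervals and P values for level and slope change are wrong.* Step 5 does not show this for level change; slope change was not examined. For a patient covariate in smaller simulations, binomial/Poisson z-ratios were 0.99–1.01 at p = 0.5 and 0.6 (patient logit SD 0.6 and 1.0). They rose to 1.3–1.5 at SD 1.8, and reached 1.08–1.51 at p = 0.7. The reported element rates imply about 0.6, though at least 70% leaves room above.

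**Conclusion.** The Poisson choice does not suit this outcome and should be changed, but its consequences are limited. What holds is a variance function that does not match the data, a patient variance component distorted in a direction the documents leave open, and less accurate ICU-specific rates (about 3–5 points mean error against 1–2). Fitted ICU rates above 100% are possible if the spread is as large as an ICC of 0.3, but did not appear at a spread matching an interquartile range of about 20 points.

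The ICU variance component and the level-change standard error are not shown to be materially wrong, and the top-5 and bottom-5 lists barely move. Complete and element measures, which have logistic models, are unaffected.

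The sizes rest on assumed patient variance, eligibility of 5 or 7 elements, and a mean share of about 0.5 over the study. The mismatch itself needs only that the measure is a share of eligible elements, the natural reading of a measure called proportional and reported in percent. This is a should-fix.

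**What to change.** In Aims 1 and 2:
- Define the numerator (elements performed that ICU-day) and the denominator (elements eligible that day), with the eligibility rule for each element.
- Replace Poisson with a multilevel segmented binomial (events/trials) logistic model, keeping the same fixed and random effects. Add a day-level random effect or a beta-binomial term for correlation among elements.
- State the scale on which the ICC is computed. Changing the model alone does not settle this.

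If rate ratios are essential, the fallback is to justify Poisson explicitly, with an offset for eligible elements, a dispersion or robust variance term, and a check that fitted rates stay below 100%.

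The cost is a few sentences. Monthly proportional rates have already been calculated from these records, so no new data should be needed. The downside is that effects become odds ratios instead of rate ratios, although this matches the scale already used for the complete and element measures.
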